5.2 Analysis of First and Second Doses

Any analyses based on first dose will only include data observed up to the time of dosing with a second dose. These summaries will be presented based on the first dose taken. The exception to this is the primary and secondary endpoints at the 2-hour time point; if a second dose is taken before the 2-hour time point, the subject will still be included in the summary at 2 hours and will be analysed as having not achieved headache pain-free or MBS-free status at 2 hours.

Any analyses based on the second dose will only include data observed on or after the time of dosing with a second dose. These summaries will be presented by treatment sequence, listed in Section 2.3. Analyses based on the second dose will be done for both the rescue and recurrence subpopulations.

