 - a. Similarly for subjects who report a first dose time with start in the future (by several hours) than indicated dosing with question “Treating Migraine with Study Med now” as “Y” at the migraine pain begin time, their efficacy assessments for first dose will be those many hours ahead of the actual assessment time for severity reporting. For example, e-diary’s 0.5 hour time point is actually 7.5 hours if the first dose time is after 7 hours of the reported migraine start time. If the reported dose time is less than 10 minutes than the time of reporting migraine as in the stated question, then these will be ignored and subject’s efficacy assessments will be used for appropriate populations of efficacy analysis. All other subjects with time difference of greater than 10 minutes will be excluded from the appropriate populations of efficacy analysis.
9. Subjects with partial second dose time on CRF and no e-diary date and time for second dose Subjects who are able to enter the first dose assessment data in e-diary but they are not able to complete the e-diary for second dose. These subjects will be able to give second dose confirmation date on the CRF at site for visit 2 but may not remember the time of the dosing for second dose after first dose. These subjects will be considered in the appropriate populations of efficacy analysis for first dose available assessments based on the assumption that they took the second dose after the minimum of 2 hours post first dose. For these subjects any assessments for first dose data after 2 hours will be unscheduled and not be summarized. To rule out this assumption, these subjects will be removed from additional sensitivity analysis as described in Section 11.6 for primary and key secondary analysis.

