11.7.1 Headache Pain-Free

The endpoint of headache pain-free will be summarized at the 0.5, 1, 1.5, 3, 4, 24, and 48-hour post-dose time points. This summary will be presented by treatment group for the ITT, mITT, and PP populations, based on first dose.

Subjects who had a mild, moderate, or severe headache at the time of dosing will be the reference subjects for this summary. Subjects missing a headache severity at baseline will not be summarized. Subjects missing a severity assessment at a post-dose time point will not be counted as pain-free.

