As described in Section 5.4, Scenario #6 subjects will be included in efficacy analysis with respect to e-diary dates and times and their relative post-dose assessments times under below rules if their respective CRF date does not match.

Subjects with partial dates entered on CRF with missing time of dosing for first dose on CRF that do not contradict the e-diary date. These subjects will be considered for efficacy analysis with respect to e-diary date and time.

Subjects with CRF first dose date is after subject answered the question for 0.5 time point due to which the questions in the e-diary look appropriate with respect to e-diary first dose date. These subjects will be considered for efficacy analysis with respect to e-diary date and time.

Subjects with indication in CRF that they had taken first dose prior to all migraine start times recorded in e-diary due to which first dose e-diary date becomes closer to or after last migraine start in the e-diary. These subjects will be considered for efficacy analysis with respect to e-diary date and time.

Subjects with different first dose times in e-diary vs on CRF. If the e-diary data is not entered retroactively by subject, then e-diary first dose dates will be in accordance with assessments completed by subject. These subjects will be considered for efficacy analysis with respect to e-diary date and time.

Subjects with CRF dates for 2nd dose are entered more than 24 hours after first dose. These subjects will be considered for efficacy analysis with respect to e-diary date and time.

Subjects with indication in CRF that they had taken second dose prior to all migraine start times recorded in e-diary due to which second dose e-diary date becomes closer to or after last migraine start in the e-diary. These subjects will be considered for efficacy analysis with respect to e-diary date and time.

Subjects with indication of taking second dose on CRF with CRF date and time but second dose date is not in e-diary. Due to this, some first dose data from e-diary assessments before time of second dose on CRF will be used for analysis. These subjects' first dose data will be considered for efficacy analysis with respect to e-diary date and time.

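### SAP 5.4, Scenario 9 voids first-dose ratings after 2 hours even when the CRF date puts the second dose on the next day; only exploratory summaries are affected

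*SAP*

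**What the plan says.** Scenario 9 in SAP 5.4 covers subjects who completed the diary for the first dose but not for the second. Of the second dose it says: "These subjects will be able to give second dose confirmation date on the CRF at site for visit 2 but may not remember the time". Their first-dose data enter the efficacy analysis "based on the assumption that they took the second dose after the minimum of 2 hours post first dose". The consequence is: "For these subjects any assessments for first dose data after 2 hours will be unscheduled and not be summarized". The known date plays no part in the rule.

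Three other places bear on this:

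- SAP 5.2 sets the general cut-off: "Any analyses based on first dose will only include data observed up to the time of dosing with a second dose".
- Appendix 16.3 deals with a second dose that has a CRF date and time but no diary entry. There, "some first dose data from e-diary assessments before time of second dose on CRF will be used for analysis".
- SAP 11.7.1 (pain-free at times other than 2 hours) fixes the denominator: "Subjects who had a mild, moderate, or severe headache at the time of dosing will be the reference subjects for this summary". It adds: "Subjects missing a severity assessment at a post-dose time point will not be counted as pain-free". SAP 11.7.3 (MBS-free) and 11.7.5 (headache relief) instead leave a subject with a missing rating out of that time point.

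Scenario 9 subjects are removed in the sensitivity analysis of SAP 11.6, but that analysis repeats only the 2-hour primary and key secondary tests.

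**The concern.** A second dose may be taken up to 24 hours after the first, so a next-day second dose is an ordinary event. When the CRF date is the next day, the assumption of dosing just after 2 hours contradicts that date for most first-dose times. Ratings at 3 and 4 hours that belong to the first dose under SAP 5.2 are then discarded.

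The visible result could be odd. A subject who is pain-free at 2, 3 and 4 hours, whose headache returns the next morning and who then takes the second dose, would be shown as pain-free at 2 hours and not pain-free at 3 and 4 hours. The time course of the first dose is a secondary objective (Protocol 5.2), although SAP 3.3 lists the 3-hour and 4-hour endpoints as exploratory, and no planned sensitivity analysis looks at those times.

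**Working it through.** The plan gives no figure for this point, so the check is a reading of the rules, a calendar bound and an illustration of size.

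**1. Rules side by side.** Under 5.2 the cut-off is the second dose itself. Under 16.3, with date and time known, ratings before the CRF time are kept. Under Scenario 9, with the date known and the time unknown, the cut-off is 2 hours whatever the date. Scenario 9 is therefore stricter than the general rule and ignores information already on the CRF.

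**2. Calendar bound.** If the CRF date is the next day and is correct, the second dose was taken no earlier than midnight:

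least gap (hours) = 24 − clock time of the first dose

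| First dose | Least gap | 3 h rating shown to precede second dose | 4 h rating shown to precede second dose |
|---|---|---|---|
| 09:00 | 24 − 9 = 15 h | yes | yes |
| 19:00 | 24 − 19 = 5 h | yes | yes |
| 20:30 | 24 − 20.5 = 3.5 h | yes | no |
| 22:00 | 24 − 22 = 2 h | no | no |

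The date settles the matter for the 3-hour rating when the first dose was before 21:00, and for the 4-hour rating when it was before 20:00. If first doses were spread evenly over the day (an assumption), these are 21/24 = 87.5% and 20/24 = 83.3% of clock times.

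**3. What a voided rating becomes.** In 11.7.1 the subject remains a reference subject because there was a headache at dosing. If a voided rating is treated as missing, the subject is not pain-free. In 11.7.3 and 11.7.5 the subject leaves the denominator at that time. In the Kaplan-Meier analyses (11.7.6 to 11.7.8), a response first reported at 3 or 4 hours is lost and the subject is censored earlier. A response already reported by 2 hours is unaffected.

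**4. Size in one arm, if the rating counts as not pain-free.** Let f be the share of an arm in Scenario 9 with a next-day date and ratings that could be kept, and r the share of these who are pain-free at 4 hours. Neither is in the documents. Assume f = 0.5% to 3% (2.85 to 17.1 of 570 subjects) and r = 20% to 80%.

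- Loss = f × r.
- Low: 0.005 × 0.20 = 0.001, or 0.1 percentage points.
- High: 0.03 × 0.80 = 0.024, or 2.4 percentage points.

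**5. The two readings compared.** Take f = 3%, r = 80% and a 20% rate among the other 552.9 subjects (all assumed):

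- Ratings kept: (552.9 × 0.20 + 17.1 × 0.80)/570 = 124.26/570 = 21.8%.
- Counted as not pain-free: 110.58/570 = 19.4%.
- Subject left out: 110.58/552.9 = 20.0%.

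Both readings lose information, and they give different answers.

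**6. Between arms.** The change in a treatment difference is f × r in the active arm minus f × r in placebo. Purely as an illustration, take equal f in both arms and set r to the planned 2-hour pain-free rates, 18.8% (200 mg) and 7.4% (placebo), which differ by 11.4 points. The change is 0.005 × 11.4 = 0.06 to 0.03 × 11.4 = 0.34 points, towards no difference. A higher r among those who re-dosed for recurrence would raise this, but the documents give no such figure.

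**The case against.** The best defence is that the CRF date is the subject's recollection at Visit 2, given by someone who could not recall the time. A single rule that voids anything doubtful, written without knowledge of the randomization code, is defensible. This stands in part: a recalled date is good evidence but not certainty. Yet Appendix 16.3 already accepts recalled CRF clock times for the same purpose, and a date is easier to recall than a time.

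Secondly, failure scoring is not stated outright. Scenario 9 calls the ratings unscheduled and says they are not summarized, and 5.4 describes unscheduled data as invalid, not missing. The subject might therefore simply be left out at that time. This stands as an ambiguity. The denominator and missing-data rules in 11.7.1 make failure the more natural reading, but the SAP does not settle it.

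Thirdly, the reach is narrow. A subject pain-free at 2 hours already has the event in the time-to-pain-free and time-to-relief analyses. Sustained pain-free (11.7.2) fails anyone who used further medication, and recurrence (11.7.11) has its own rule for an unrecorded severity. All of this stands.

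A reader might infer that the active arms must lose more, since a second dose for recurrence requires pain freedom at 2 hours and the planning rates are 18.8% and 7.4%. The documents do not support that. Those rates describe 2-hour responders, not next-day users who forgot the time. Second doses also serve rescue in non-responders, who are 100 − 18.8 = 81.2% of the 200 mg arm and 100 − 7.4 = 92.6% of the placebo arm on the same rates.

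**Conclusion.** The point holds as a minor defect in data handling. Scenario 9 discards first-dose ratings that the recalled CRF date places before the second dose, which is out of line with SAP 5.2 and Appendix 16.3. The effect is confined to exploratory summaries after 2 hours, chiefly the 3-hour and 4-hour proportions.

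A reader might also infer that the confirmatory result is at risk. It is not: Scenario 9 keeps the 2-hour rating, and SAP 11.6 repeats the 2-hour tests without these subjects.

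The loss of 0.1 to 2.4 percentage points in an arm rests on assumed values of f and r and on reading 11.7.1 as failure scoring. The number of subjects concerned and any imbalance between arms cannot be known from the documents. If there were more such subjects on lasmiditan who were pain-free at these times, the bias would be towards no difference.

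**What to change.** Replace the last part of the Scenario 9 rule with wording such as:

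> In all cases keep first-dose ratings up to and including the 2-hour assessment. If the CRF second-dose date is later than the first-dose date, also keep later first-dose ratings time-stamped before 00:00 of the CRF second-dose date and treat the rest as unscheduled. If the two dates are the same, treat all ratings after 2 hours as unscheduled.

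The first sentence is essential. With a first dose at or after 22:00, the 2-hour rating falls at or after midnight. A midnight cut-off alone would void a rating that is kept now, and SAP 5.3 and 11.2 would turn a 2-hour responder into a primary-endpoint failure.

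Also state in SAP 11.7.1 whether a rating made unscheduled counts as not pain-free or removes the subject from that time point.

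The cost is a few sentences and one programming condition; the CRF date and the diary assessment times are already collected. The drawback is reliance on a recalled date, as 16.3 already relies on recalled times. Repeating the 3-hour and 4-hour summaries without Scenario 9 subjects would show whether that matters.

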6 DISPOSITION OF SUBJECTS AND DISCONTINUATIONS

The following will be summarized overall and by treatment sequence, for all subjects, as counts and percentages of all subjects:

- Subjects randomized
- Subjects with confirmed eligibility
- Subjects treated

- Subjects treated with second dose
 - Treated with second dose for rescue
 - Treated with second dose for recurrence
- Subjects in each of the analysis populations:
 - Randomized population
 - ITT population
 - mITT population
 - PP population
 - ITT-2nd Dose population; overall, for rescue, and for recurrence
 - Safety population
 - Safety-2nd Dose population
- Subjects who completed the study
 - Treated
 - Not treated
 - Reason for not having been treated
 - No Migraine
 - No access to study medication during migraine
 - No eligible migraine within 8 weeks
- Treated but did not return for Visit 2 (EOS)
- Discontinued subjects
 - Treated
 - Not treated
- Reasons for subject discontinuation
 - Adverse event
 - Death
 - Lost to follow-up
 - Non-compliance with protocol requirements
 - Pregnancy
 - Subject request
 - Investigator request
 - Sponsor request
 - Randomization failure
- Randomized subjects at each investigative site
- Subjects with treatment unblinded by site
- Subjects with headache severity data at 2 hours post first dose
- Subjects with MBS data at 2 hours post first dose

The number and percentage of subjects in each disposition category will be presented; percentages will be based on the number of randomized subjects. Percentages for the number of subjects randomized will be based on the total number of subjects who enrolled in the study. Percentages for the number of subjects treated with a second dose for rescue or recurrence will be based on the total number of subjects who took a second dose. Percentages for the treated status of discontinued subjects will be based on the number of subjects who discontinued. For discontinuation reasons, percentages will be based on the number of subjects who discontinued. Subjects' inclusion in the analysis populations will be listed. Disposition data, and all subjects who discontinue from the study, will be presented in listings.

7 PROTOCOL DEVIATIONS

The number and percentage of subjects with protocol deviations leading to exclusion from the PP population will be presented by reason for exclusion and treatment sequence. Summaries will be run on all confirmed eligible subjects in the Randomized population and on the mITT population, with percentages based on the number of subjects in those populations. All deviations will be listed.

8 DEMOGRAPHICS AND BASELINE CHARACTERISTICS

8.1 Demographics

The following will be summarized by treatment group and overall for the ITT, mITT, PP, and Safety populations, and by treatment sequence and overall for the Randomized, ITT-2nd Dose, and Safety-2nd Dose populations.

- Age
- Gender
 - Female
 - Male
- Race
 - American Indian or Alaska Native
 - Asian
 - Black or African American
 - Native Hawaiian or other Pacific Islander
 - White
 - Other
 - Multiple
- Ethnicity
 - Hispanic or Latino
 - Not Hispanic or Latino
 - Not Reported
 - Unknown
- Height (in)
- Weight (lb)
- BMI (kg/m²)
- Smoking history
 - Never
 - Former
 - Currently
- Family history of coronary artery disease
 - Yes
 - No
- Cardiovascular Risk factors by Gender and Male greater than or equal to 40
- Duration of migraine history (years)
- Average migraines per month during the past 3 months from the date of Visit 1
- Experiencing migraine attacks both with and without aura (yes or no)
- Use of medication that reduces the frequency of migraine episodes as recorded in IVRS.

Age will be calculated using the difference in days between the date of birth and the date of informed consent.

BMI will be calculated as:

$$\text{Weight (lb)} / \text{height (in)}^2 * 703$$

Duration of migraine history, presented in years, will be calculated using the difference in days between the date of migraine diagnosis and the date of informed consent.

All demographic data will be presented in a listing.

8.2 MIDAS

Migraine Disability Assessment (MIDAS) total scores will be summarized by treatment sequence for the Randomized, ITT, and mITT populations. The MIDAS is a five-item questionnaire; the MIDAS total score is calculated as the sum of the answers to all five questions. The specifics of the questionnaire are detailed in Appendix 3 of the Protocol. The total MIDAS score will be calculated at each site on the questionnaire and any analytical missing data imputation will not be performed for missing value. The total score will be calculated based on the available score for each subject.

Additionally, descriptive statistics on the number of days subjects experienced headaches in the past three months and the average pain of those headaches will be presented. Average pain is measured on a scale from 0 to 10, where 0 is no pain at all and 10 is pain as bad as it can be.

Answers to individual MIDAS questions will be presented in a listing.

8.3 Medical History

Medical history will be summarized by treatment group for the Safety population, and treatment sequence for the Safety-2nd Dose population. Medical history will be coded using the Medical Dictionary for Regulatory Activities (MedDRA), version 18.0, and sorted alphabetically by system organ class and then preferred term by frequency. Subjects with multiple occurrences of the same medical history term will be counted once within the corresponding system organ class and preferred term.

All medical history will be presented in a listing.

8.4 Migraine Treatment History

Migraine treatment history will be summarized by treatment sequence. The summaries will be presented for the ITT and mITT populations. Migraine treatment history will be coded using the WHO Drug Dictionary, version WHODDE 01MAR2015E, and sorted by frequency of preferred name. Subjects with multiple occurrences of the same medication will be counted once within the corresponding preferred name.

All migraine history and migraine characteristics data will be presented in listings.

8.5 Characteristics of Treated Migraine Attacks

The following will be summarized by treatment group for the mITT and ITT populations, and by treatment sequence for the ITT-2nd Dose population.

- Time to dosing (or second dosing) from the start of migraine attack (hours)
- Time to dosing (or second dosing) from the start of moderate or severe pain (hours)
- Baseline migraine severity
 - Severe (3)

- Moderate (2)
 - Mild (1)
 - None (0)
- Baseline associated symptoms (yes or no)
 - Nausea
 - Phonophobia
 - Photophobia
 - Vomiting
 - None
- Baseline most bothersome symptom
 - Nausea
 - Phonophobia
 - Photophobia
- Accompanying aura at time of first dose (yes or no)
- Second dose of study drug taken before the 2-hour assessment (yes or no)
- Other medications taken to treat migraine (yes or no)
 - No
 - Yes, before 2-hour assessment
 - Yes, after 2-hour assessment
- Number of days of school or work missed due to migraine

Time to dosing from start of the migraine attack (hours) will be calculated as:

date/time of dosing –
date/time of start of the acute migraine attack

Time to dosing from start of moderate or severe pain (hours) will be calculated as:

date/time of dosing –
date/time of start of moderate to severe pain

Date and time of dosing will be taken from the subject e-diary.

9 PRIOR, CONCOMITANT, AND POST-DOSE MEDICATIONS

The frequency and percentage of prior, concomitant, and post-dose medication use will be presented by treatment group based on first dose and summarized for the Safety population. Medications will be coded using the WHO Drug Dictionary, version WHODDE 01MAR2015E, and sorted by frequency of preferred name.

Prior medications are those taken on or after the date of Visit 1 and before the day of any dosing of study drug. Concomitant medications are those taken on the day of, or within two days after, any dose of study drug. Post-dose medications are those taken after two days after any dose of study drug and on or before the end of the study. (Sources of these dates are elaborated in Section 5.)

Medications missing a start and end date will be considered prior, concomitant, and post-dose. Medications missing a start or end date will be considered as having been taken in all applicable time points based on the non-missing date. See Appendix 1 for derivations related to partial dates and times.

All medication data will be presented in a listing.

10 TREATMENT COMPLIANCE

Both the first and second dose of study drug requires taking two tablets for each dose. Compliance with a prescribed dose can be either 50% (the subject only took one of the tablets), or 100% (the subject took both tablets for the first dose). Compliance is not calculated for subjects who did not take a dose. If the CRF entries leave the number of tablets taken per dose unclear, 50% compliance will be assumed for one or both doses.

Descriptive statistics will be used to summarize compliance separately for subjects who took a first dose, and for subjects who took a second dose.

Subjects are asked not to use a second dose until at least two hours after the first dose. The time from first to second dose will be summarized with descriptive statistics for subjects who took a second dose.

Compliance data will also be presented in a listing.

